8 TOXICITIES AND DOSE MODIFICATION

Every effort should be made to administer Q-Urol/Placebo at the planned dose and schedule. In the event of study treatment toxicity, dosing may be interrupted, delayed, and/or discontinued. In the event of multiple toxicities, treatment/dose modifications should be based on the worst toxicity observed (CTCAE v5.0) and/or the most conservative recommendation for any given toxicity. Patients are to be instructed to notify Investigators at the first occurrence of any adverse symptom.

All dose holds must be clearly documented in the patient's medical chart and in the CRF. Appropriate follow-up assessments should be done until adequate recovery occurs as assessed by the Investigator.

8.1 Dose Modifications

While dose reductions are not permitted on trial, dose interruptions for study treatment-related AEs are allowed as deemed necessary by the treating physician. Doses of Q-Urol/Placebo that were not administered due to toxicity will not be replaced. If a toxicity-

Version Date: 11APR2023

related dose delay extends over 12 days, treatment will be discontinued permanently and the patient should be removed from the study.

Study therapy may be held for any treatment-related adverse events, grade ≥ 2 as deemed necessary by the treating investigator. Upon resolution of the treatment-related adverse event, study therapy may be resumed at the prior dose level and frequency.

If a subject on study therapy experiences a grade \geq 3 SAE attributed to study drug, study therapy will be discontinued.

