7.2.3 Accountability and Compliance

Information pertaining to study drug compliance (i.e., date, time, and dose) will be recorded by patients on the drug diary (see Appendix 6) and recorded in the corresponding electronic case report form (eCRF) by the study team. A member of the study team will review patient drug compliance and provide patient re-education as required. Any reason for non-compliance will be documented in the subject's research chart and the corresponding eCRF. At the discretion of the principal investigator, a subject may be discontinued from the trial for non-compliance with study visits or study drug.

Subjects will be required to return any unused medication or empty bottles at the end of study therapy. Excess or unused study drug should be returned to the investigative site for accounting and destroyed in accordance with GCP after drug accountability has been performed. The total number of capsules dispensed, returned, and documented as taken will be reconciled to support drug accountability. Treatment compliance will be calculated and recorded for the study drug. It will be recorded as a percentage defined as the number of doses taken divided by the expected number of doses taken multiplied by 100%.

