7.4.1 Criteria for discontinuation of treatment ("off-treatment")

Patients may withdraw from treatment or the study overall at any time at their own request, or they may be withdrawn at the discretion of the Investigator or Sponsor for safety, behavioral reasons, or the inability of the patient to comply with the protocol-required schedule of study visits or procedures. In addition to the drug-specific discontinuation criteria listed in Dose Modification Section, the following will result in treatment discontinuation:

Version Date: 11APR2023

- Unacceptable Toxicity
- Subject requests to discontinue the study treatment and/or study procedures.
- Non-compliance as defined as missing ≥ 30% of the required Q-Urol/placebo doses. At the discretion of the principal investigator, the subject may be permitted to continue on treatment after the first noted occurrence of non-compliance if the subject is re-educated on treatment administration and compliance can be achieved within a reasonable timeframe.
- Significant protocol violation
- Study terminated by investigator sponsor
- Lost to follow-up

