7.4.2 Criteria for discontinuation of study ("off study")

Subjects will be taken off study for the following:

- Completed study end of treatment visit.
- Screen failure.
- The subject is lost to follow-up.
- If, in the investigator's opinion, the continuation of the trial would be harmful to the subject's well-being.
- Development of intercurrent illness or situation which would, in the judgment of the investigator, significantly affect assessments of clinical status and trial endpoints.
- Participant requests to be withdrawn from the study
- Death

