10.3 End of Treatment

An End of Treatment visit will occur six weeks after brachytherapy. At this visit, the patient will discontinue Q-Urol, return any remaining medication, the pain medication diary, and the dosing diary for medication reconciliation. For End of Treatment procedures the Schedule of Events and the Assessments Section.

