11.5 Questionnaire administration

All questionnaires will be completed in the clinic by the patient prior to starting study therapy and after completing six weeks of daily Q-Urol/Placebo therapy.

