12.3.2 Evaluable for response

A modified intent-to-treat data set will be used to assess efficacy. Subjects who have successfully undergone brachytherapy and received one dose of Q-Urol will be evaluable for response. Subjects who fail to undergo brachytherapy or begin Q-Urol therapy will be replaced. Those who do not complete the end of treatment patient questionnaires will be considered treatment failures.

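### Section 8.1 takes patients with a long toxicity delay off study, not only off drug, so a six-week primary score that could be collected would probably be imputed; the effect is small and its direction unknown

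*Combined protocol and SAP*

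**What the plan says.** Section 8.1 attaches two consequences to a toxicity-related delay of more than 12 days: "treatment will be discontinued permanently and the patient should be removed from the study". The same section, for a grade 3 or higher SAE attributed to study drug, stops study therapy and says nothing about leaving the study.

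Section 7.4.1, the off-treatment section, opens its list with "In addition to the drug-specific discontinuation criteria listed in Dose Modification Section, the following will result in treatment discontinuation". One item in that list is "Non-compliance as defined as missing ≥ 30% of the required Q-Urol/placebo doses". Section 7.4.2 begins "Subjects will be taken off study for the following" and gives seven reasons. A long toxicity delay is not among them.

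On data collection, the Schedule of Events places the questionnaires, including the NIH-CPSI, at screening and Day 43 only. Section 10.3 times the later visit from the implant: "An End of Treatment visit will occur six weeks after brachytherapy". Section 11.5 ties the later questionnaire to the drug course: "after completing six weeks of daily Q-Urol/Placebo therapy".

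On analysis, 12.3.2 uses a modified intent-to-treat set that a patient enters after brachytherapy and one dose. Replacement is limited: "Subjects who fail to undergo brachytherapy or begin Q-Urol therapy will be replaced". Section 13.2.2 multiply imputes missing end-of-treatment NIH-CPSI scores, with a worst-observed-value sensitivity analysis. Section 12.3.2 instead classes patients without final questionnaires as failures of treatment.

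**The concern.** Stopping study drug and stopping data collection are different events, and 8.1 joins them for one group of patients. Those patients count in the primary analysis, are not replaced, and have no post-baseline NIH-CPSI before Day 43 on which imputation could draw. Their scores would be missing because of a removal rule, not because they could not be obtained.

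Missing scores of this kind may be informative. Men removed for a long toxicity delay may differ in symptoms from men who stayed. If they do, and if removal is more frequent in one arm, imputing them as though they resembled completers shifts the estimated difference. Site staff also lack one clear answer on whether such a patient returns at Day 43.

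**Working it through.** **1. The passages side by side.**

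| Event | Section | Stated consequence |
|---|---|---|
| Toxicity delay over 12 days | 8.1 | Drug stopped and patient removed from study |
| Dose-modification criteria in general | 7.4.1 | Treatment discontinuation |
| Drug-attributed grade 3 or higher SAE | 8.1 | Study therapy stopped |
| At least 30% of doses missed | 7.4.1 | Treatment discontinuation |
| Toxicity delay over 12 days | 7.4.2 | Not listed as off-study |

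The course is six weeks, or 42 days. A 13-day delay is 13/42 = 31% of it, and the 30% threshold is 0.30 × 42 = 12.6 days. One patient can therefore meet an off-treatment rule (7.4.1) and an off-study rule (8.1) for the same missed doses.

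**2. When the score is at risk.** To exceed 12 days before Day 43, a delay must start by about Day 43 − 13 = Day 30. Later delays do not trigger the rule before the visit.

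**3. The plan's own figure.** Section 13.2.1 states 90% power for 70 per arm, a 0.5 SD effect, an interim at 21 per arm, and bounds of −1.16 and 2.85 with a final critical value of 1.67. Simulating this design gives 90.0 to 90.1%, so the stated figure reproduces.

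**4. Bias in the primary contrast.** Assume that removed patients score *g* SD worse than completers and that each is imputed, on average, at the completer mean of his own arm. If a share *f* of an arm is removed, that arm's mean is understated by *f* × *g*. For control minus treatment:

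bias = (number missing on Q-Urol − number missing on placebo) / 70 × *g*

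A positive value favours Q-Urol. The documents supply none of the removal counts below, and *g* = 0.5 to 1.0 SD is assumed.

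| Missing, Q-Urol v placebo | g = 0.5 | g = 1.0 | Share of 0.5 SD target |
|---|---|---|---|
| Equal (for example 4 v 4) | 0 | 0 | 0 |
| 2 v 1 | 1/70 × 0.5 = 0.007 | 1/70 × 1.0 = 0.014 | 1–3% |
| 7 v 4 | 3/70 × 0.5 = 0.021 | 3/70 × 1.0 = 0.043 | 4–9% |
| 2/15 v 1/15 of each arm | 1/15 × 0.5 = 0.033 | 1/15 × 1.0 = 0.067 | 7–13% |

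The sign reverses if placebo loses more patients, or if removed patients score better than completers. The last row uses the adverse-event counts of the 30-man quercetin trial (2.3 and 3.1.2). It is probably too high as a removal rate: those events were a headache, mild tingling and a rash that resolved on stopping, and none is described as a hold of more than 12 days.

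**5. Power.** If scores are lost equally and at random and imputation recovers nothing, power at 0.5 SD is about 89.7% with 1 lost per arm, 88.6% with 4 and 87.2% with 7.

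**The case against.** The strongest reply is that 8.1 and 7.4.1 can both be obeyed. Leaving the study implies leaving treatment. Section 7.4.1 never says that its events stop drug only; its list includes loss to follow-up, which 7.4.2 also counts as off-study. Section 7.4.2 does not call itself exhaustive, and its investigator-judgement items could cover some long delays. This largely stands. What remains is an off-study trigger in 8.1 that the off-study section omits, not two instructions that cannot both be followed.

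Second, no passage says that a removed patient skips the six-week questionnaire. Section 8 calls for follow-up until recovery, and adverse events are collected to 30 days after the last dose, so contact may continue. This stands as well: loss of the score is an inference from removal together with the absence of any other scheduled questionnaire. Continuing contact also suggests that the score could be obtained.

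Third, 13.2.2 does not specify the imputation model. One that uses baseline scores or the pain diary could shrink the bias below the figures shown.

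Fourth, a reader might infer that 7.2.3 has the same fault, since "a subject may be discontinued from the trial for non-compliance with study visits or study drug". The documents do not support that. The clause is permissive and left to the principal investigator, and the opening of 7.4.1 also allows withdrawal from the study at discretion. Discretionary withdrawal is not part of this point.

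**Conclusion.** The point holds as a minor, avoidable weakness. Followed as written, 8.1 probably leaves a patient in the modified intent-to-treat set without a primary score that a visit timed from brachytherapy could have supplied.

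At the assumed low rate of 2 v 1 of 70, the bias is 1 to 3% of the target effect. Larger values need removal rates for which the documents give no evidence. Every figure rests on assumed counts, an assumed 0.5 to 1.0 SD gap and within-arm imputation from completers.

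Two stronger readings are tempting. One is that the rule favours Q-Urol; the documents do not fix the split by arm or the prognosis of removed patients, so the direction is unknown. The other is that removed patients drop out of the primary analysis; they do not, because 12.3.2 keeps them and 13.2.2 imputes their scores.

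**What to change.** Leave every rule for stopping study drug, discretionary withdrawal (7.2.3 and the opening of 7.4.1) and the 7.4.2 criteria as they are. No view is taken on the 12-day limit. Then:

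1. Reconcile 8.1 with 7.4.1 and 7.4.2 so that stopping study drug for a long delay does not by itself end study participation.
2. State in 8.1 and 11.5 that patients who stop study drug early still complete the questionnaires at the six-week post-brachytherapy visit, unless they withdraw or are taken off study under 7.4.2 or by discretion. Item 1 alone is not enough, because 11.5 ties the questionnaire to completing the drug course.
3. Use those scores in the modified intent-to-treat primary analysis.
4. As a separate wording point, align the failure label in 12.3.2 with the imputation rule in 13.2.2. The label has no numerical value in a comparison of means.

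The cost is a few sentences and one already scheduled visit for a few patients off drug. The change does not buy power and may slightly dilute the effect. If a share of Q-Urol patients stop and then score as placebo patients do, simulated power is about 89.4% at 1% stopping, 88.3% at 3% and 87.0% at 5%. At 10% it is about 83.6%, against about 87.2% if 10% of scores in each arm were instead missing at random. That dilution belongs to the modified intent-to-treat comparison the plan has chosen. The gain is less reliance on imputation.

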8.2 Supportive Care

All supportive measures consistent with optimal patient care may be given throughout the study.

8.3 Contraception

Subjects will be instructed to abstain from sexual intercourse for the first two weeks after brachytherapy implantation. After the first two weeks, subjects may engage in sexual intercourse but should use a condom for the duration of study participation and for 5 days after the last dose of study therapy. In addition, female partners of childbearing potential should also use a highly effective contraceptive method during the same period.

Acceptable highly effective contraceptive methods include:

- Bilateral tubal occlusion
- Intra-uterine devise (IUD) or hormone-releasing system (IUS)
- Any hormonal (estrogen combined with progesterone or progesterone alone) contraception associated with inhibition of ovulation: implanted, oral, intravaginal, transdermal, or injectable
- Spermicide in combination with a compatible barrier method (i.e. diaphragm, sponge, or male or female condoms)
- Abstinence from heterosexual intercourse.

9 SCHEDULE OF EVENTS

The Schedule of Events table provides an overview of the protocol visits and procedures. Refer to the Study Procedures section of the protocol for detailed information on each assessment required for compliance with the protocol. The Investigator may schedule visits (unplanned visits) in addition to those listed in the Schedule of Events table in order to conduct evaluations or assessments required to protect the wellbeing of the patient. This Schedule of Events will be followed for the entire study.

Version Date: 11APR2023

Table 1: Schedule of Events

	Screening	On Treatment Period						Post-Treatment Period	
Protocol Activities		Day 1	Day 8	Day 15	Day 22	Day 29	Day 36	EOT (Day 43)	30 days post EOT
Visit Window	(-90 days)		(± 2 days)	(± 2 days)	(± 3 days)	(± 3 days)	(± 3 days)	(+7 days)	(± 7 days)
Informed Consent	X								
Demographics	X								
Medical History	X								
Baseline Characteristics ¹	X								
Eligibility Criteria	X								
Randomization	X								
Clinical Assessments				•	•				
Vital Signs ²	X	X						X	
Physical Exam	X	X						X	
ECOG Score ³	X	X							
NCCN Risk Stratification ⁴	X								
Charlson Comorbidity Index ⁵	X								
Phone Call ⁶			X	X	X	X	X		X
Adverse events		X							
Concomitant Medications		X							

Version Date: 11APR2023

	Screening	On Treatment Period					Post-Treatment Period		
Protocol Activities		Day 1	Day 8	Day 15	Day 22	Day 29	Day 36	EOT (Day 43)	30 days post EOT
Visit Window	(-90 days)		(± 2 days)	(± 2 days)	(± 3 days)	(± 3 days)	(± 3 days)	(+7 days)	(± 7 days)
Laboratory Studies									
Hematology ⁷	X								
Chemistry ⁸	X								
Testosterone	X							X	
Inflammatory marker ⁹	X							X	
Subject Materials									
Patient questionnaires ¹⁰	X							X	
Q-Urol/Placebo dosing diary ¹¹		X						X	
Pain management diary ¹²		X						X	
Study Therapy	•								
Q-Urol/Placebo ¹³					X				
Brachytherapy		X							

¹ Appendix 9.

² Vital signs to include weight and height (height will be measured at screening only), blood pressure, pulse rate and temperature.

³ Appendix 11.

Version Date: 11APR2023

⁴ Appendix 8. NCCN Risk Stratification may be taken from the initial consultation note where brachytherapy was recommended.

⁵ Appendix 10.

⁶ An appropriately trained and delegated study team member will contact subjects on treatment weekly to assess adverse event and concomitant medication information, to answer subject questions, and to ensure compliance with study medication and procedures. 30 days after the last dose of study drug, a study team member will contact subjects to assess adverse event information.

⁷ CBC with differential and platelets.

⁸ Complete Metabolic Panel including: Sodium, Potassium, Chloride, Carbon Dioxide, Alkaline Phosphatase, Aspartate Aminotransferase, Alanine Aminotransferase, Urea Nitrogen, Glucose, Creatinine, Calcium, Protein, Albumin, Bilirubin, Anion Gap.

⁹ Inflammatory markers include: erythrocyte sedimentation rate, C-reactive protein, prostate-specific antigen (PSA)

¹⁰ Questionnaires include: National Institutes of Health-Chronic Prostatitis Symptom Index (NIH-CPSI), The Expanded Prostate Cancer Index Composite (EPIC), The International Prostate Symptom Score (I-PSS), Rectal Function Assessment Score (R-FAS), The Sexual Health Inventory for Men (SHIM) Questionnaire.

¹¹ A Q-Urol/Placebo dosing diary will be dispensed on the day of brachytherapy and returned completed at the EOT visit (Appendix 6).

¹² Patients will be asked to maintain a diary of the daily use of medications taken for prostate pain for 28 days post-brachytherapy (Appendix 7).

¹³ Q-Urol/Placebo will begin after brachytherapy placement.

Version Date: 11APR2023

10 STUDY PROCEDURES

10.1 Screening

For screening procedures see the Schedule of Events and the Assessments Section. Screening activities may only begin after a subject has signed consent. All screening activities must take place within 90 days prior to brachytherapy unless otherwise noted.

10.2 Treatment Period

Once a subject has completed screening, has been found to be eligible, and has been registered, treatment procedures may begin. On the same day, but after brachytherapy, patients will begin Q-Urol or placebo. Patients on treatment will be contacted weekly by a trained and delegated study member to assess adverse events, concomitant medications, and to answer questions to ensure protocol adherence. See the Schedule of Events and the Assessments Section for treatment period procedures.

10.3 End of Treatment

An End of Treatment visit will occur six weeks after brachytherapy. At this visit, the patient will discontinue Q-Urol, return any remaining medication, the pain medication diary, and the dosing diary for medication reconciliation. For End of Treatment procedures the Schedule of Events and the Assessments Section.

11 STUDY ASSESSMENTS

Every effort should be made to ensure that the protocol-required tests and procedures are completed as described. However, it is anticipated that from time to time there may be circumstances, outside of the control of the Investigator that may make it unfeasible to perform the test. In these cases, the Investigator will take all steps necessary to ensure the safety and well-being of the patient. When a protocol-required test cannot be performed, the Investigator will document the reason for this and any corrective and preventive actions that he or she has taken to ensure that normal processes are adhered to as soon as possible.

11.1 Physical Examinations and Vital Signs

Patients will have physical examinations to include major body systems, vital signs, assessment of ECOG performance status (see Appendix 1), weight and height (height will be measured at screening only) at the time points described in the Schedule of Events. If necessary to facilitate scheduling, the physical exam may occur one day prior to study treatment.

Vital signs, including blood pressure, pulse rate, and temperature will be also recorded at the time points described in the Schedule of Events.

11.2 Baseline Characteristics

The following baseline characteristics will be collected from patients at screening (see also Appendix 9):

Version Date: 11APR2023

- Does the patient have a history of Coronary Artery Disease?
- Has the patient had bacterial prostatitis that went away with antibiotics?
- Does the patient have any family history of prostatitis?
- Alcohol history (never used alcohol, current alcohol user, former alcohol user)
- Smoking history (never smoked, current smoker, former smoker)
- Pack years (average number of packs per day and number of years smoked)
- Current employment status (employed, retired, student, unknown, other)
- Insurance status (private insurance, Medicare, Medicaid, VA, military, not insured, self-pay, unknown, other)
- Prostate volume
- Post-void residual urine volume if available
- Prior use of alpha-blockers for symptoms
- The extent of prostate cancer, including location of the cancer relative to the prostate gland capsule

11.3 Adverse Events

Adverse events experienced during trial participation will be collected per the Schedule of Events and Adverse Events Section. Each study participant will be questioned about the occurrence of adverse events in a non-leading manner. Should the treating investigator feel that the adverse event is attributed to study therapy, then dose modification guidelines in the Dose Modification Section will be followed.

11.4 Laboratory Assessments

Samples for all laboratory assessments will be drawn at the time points indicated in the Study Calendar and when clinically indicated. All safety laboratory analyses will be performed by the local laboratory. All safety laboratory assessments must be reviewed by the treating investigator prior to study drug administration.

Table 2: Laboratory Assessments

Laboratory Assessments					
CBC with Platelet Count and Differential	White Blood Cell Count				
	Hemoglobin				
	• Platelets				
	Absolute Neutrophil Count				
	Absolute Lymphocytes				
Complete Metabolic Panel (Chemistry)	Sodium				
	Potassium				
	Chloride				
	Carbon Dioxide				
	Alkaline Phosphatase				

Version Date: 11APR2023

	Aspartate Aminotransferase
	Alanine Aminotransferase
	Urea Nitrogen
	Glucose
	Creatinine
	Calcium
	• Protein
	Albumin
	Bilirubin
Endocrine	Testosterone
Inflammatory Markers	Erythrocyte sedimentation rate
	C-reactive protein
	• Prostate-specific antigen (PSA)

